9.4. Other Restrictions and Precautions

- Medications with known or potential anti-HCV activity other than the assigned study treatment are prohibited from study treatment initiation until 12 weeks' post-treatment.
- Use of any medication or herbal product not prescribed by the investigator or a licensed physician is prohibited.
- Methadone and buprenorphine can be used with caution.
 Long-term treatment (≥ 2 weeks) with agents that are immunosuppressive, or have a high risk for nephrotoxicity or hepatotoxicity, should be discussed with the study team.

9.5. Contraception methods

Since the safety of DAAs during pregnancy is not known and results indicated a teratogenic potential for ravidasvir (PPI-668) in rabbits at doses of 100mg/kg/day or more, women of child bearing potential must use a highly effective contraceptive method from at least 2 weeks before treatment initiation and until 1 month after the last dose of study medications. Highly effective acceptable methods of contraception include intrauterine device (IUD), intrauterine hormone-releasing system (IUS), hormonal contraceptives, bilateral tubal occlusion, vasectomised partner and sexual abstinence. Pregnant women will be excluded during screening evaluations.

9.6. Assessment of adherence

This study will use a combination of two measures of adherence:

- 1. Subject diary card
- 2. Pill count

At each study visit, adherence will be assessed by pill count. Study drug and dosing diary will be reconciled at all on-treatment visits by the site staff/investigator in order to monitor the subject's adherence with the study drug regimen.

Subjects must be instructed to bring back all bottles of study drugs in the original container at each study visits.

9.7. Discontinuation and interruption of treatment

Treatment may be discontinued:

- upon request of the subject, following counselling on the potential consequences and risks of antiviral discontinuation
- upon request of the primary care provider if s/he thinks that the it is no longer in the best interest of the subject,
- if, after discussion with the study team, the investigator judges that the subject is at significant risk of failing to comply with the provisions of the protocol thus compromising the validity of the study results,

- in case of HCV virological failure,
- in occurrence of serious adverse events deemed to be related to the study drugs or possibly interfering with therapy and upon consultation with the DSMB. Patient's follow-up will continue as follow-up visits in protocol and unscheduled visits are allowed as decided by investigators.
- upon recommendation of the Data and Safety Monitoring Board (DSMB) and,
- at the discretion of the IRB, relevant regulatory agency, any other government agency as part of their duties to protect the welfare of subjects

The study team must be informed, as soon as possible, when a subject comes off study treatment due to an AE. Restart of treatment after any interruption must be discussed and agreed on a case by case basis with the investigator and agreed with the sponsor.

Subjects who prematurely discontinue study treatment (i.e., prior to completion of their assigned dosing period) will complete all end of treatment evaluations, will remain on study and complete all post treatment visits, except if they have withdrawn consent.

If applicable, additional unscheduled post-treatment safety follow-up will be determined by the site investigator.

In stage 2, the following treatment stop criteria^[65] will apply for any patient from stage 2 study with:

- ALT/AST > 8x ULN
- ALT/AST remains > 5x ULN over 2 wks
- ALT/AST > 3x ULN & T Bili > 2x ULN or INR > 1.5
- ALT/AST > 3x ULN with symptoms (e.g. fatigue, nausea and vomiting, right upper quadrant of abdomen pain, fever, rash) or eosinophilia

Generally, rechallenge of subjects with significant ALT/AST elevations (>5xULN) should not be attempted. If such subjects are rechallenged, they should be followed closely. Rechallenge can be considered if the subject has shown important benefit from the drug and other options are not available or if substantial accumulated data with the test drug do not show a potential for severe injury. The subject should be made aware of the potential risk, and consent to the rechallenge, and the institutional review board consulted.

A DSMB meeting will be set up in case one patient meets any of the above listed criteria, which is considered as a major safety signal.

10. Baseline Assessments

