15.3. Grading of Adverse Event severity

All toxicities and intensity of AEs will be evaluated by the investigator ad graded according to the DAIDS AE grading table version 2.0 / November 2014 (see Appendix II).

The decision to continue, put the study on hold or discontinue therapy is applicable to both drugs, sofosbuvir and ravidasvir, whatever the assumed relationship between one or both drugs and an adverse event. Using either drug alone may not only result in virological failure, but also may select resistance mutations which may jeopardize future therapy.

- Grade 1 and 2 Adverse Event
 - o Continue study treatment
- Grade 3 Adverse Event
 - For clinical events, or while awaiting a repeat assessment / confirmation as soon as possible (at most within 1 week) of an abnormal laboratory test the study treatment can be continued upon the judgment of the site investigator.
 - If repeat assessment of an abnormal laboratory test confirms Grade 3 toxicity and if the site investigator considers that the toxicity is possibly, probably, or definitely related to one or both study drugs, the treatment should be put on hold and laboratory values will be followed weekly and notified to the research team within 72 hours. Management of adverse events probably not related to study drugs will be determined on a case-by-case basis at the discretion of the site investigator.

- If toxicity resolves to ≤ Grade 2 within 7 days, study treatment can be restarted for the remaining planned treatment duration.
- If Grade 3 toxicity persists for >7 days, restart of the treatment will be under judgement of investigator in consultation with the sponsor.

If Grade 3 recurs to > Grade 3 after reintroduction of study drugs, treatment must be permanently discontinued. The site investigator and the study team will consult each other on treatment options on a case-by-case basis.

• Grade 4 Potentially-Life-Threatening Adverse Event

- If the site investigator and the study team consider that the adverse event is possibly, probably, or definitely related to one of the study drugs, the dual study treatment should be withheld and the study team be notified within 24 hours. For abnormal laboratory tests, repeat assessment/confirmation should be done as soon as possible (at most within 1 week).

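### Sections 9.7 and 15.3 of the protocol give different rules for stopping and restarting treatment, and neither says which one governs

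*Protocol*

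**What the plan says.** **Section 9.7 (Discontinuation and interruption of treatment).** Restart of "treatment after any interruption must be discussed and agreed on a case by case basis with the investigator and agreed with the sponsor". For stage 2 it adds four liver stop criteria, which "will apply for any patient from stage 2 study with":

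- ALT/AST above 8x ULN;
- ALT/AST staying above 5x ULN over 2 weeks;
- ALT/AST above 3x ULN with total bilirubin above 2x ULN or INR above 1.5;
- ALT/AST above 3x ULN with symptoms or eosinophilia.

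In general, "rechallenge of subjects with significant ALT/AST elevations (>5xULN) should not be attempted". Where rechallenge is nevertheless considered, "The subject should be made aware of the potential risk, and consent to the rechallenge, and the institutional review board consulted". A single patient meeting any criterion leads to a DSMB meeting, "which is considered as a major safety signal".

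**Section 15.3 (Grading of Adverse Event severity).** At Grade 1 and 2 the instruction is "Continue study treatment". At Grade 3, for clinical events or while a repeat laboratory test is awaited (at most 1 week), "the study treatment can be continued upon the judgment of the site investigator". If the repeat confirms Grade 3 and the investigator "considers that the toxicity is possibly, probably, or definitely related to one or both study drugs, the treatment should be put on hold". Grade 4 treatment is withheld if the event is judged at least possibly related. Three lines then deal with restart: Grade 3 that settles within 7 days, Grade 3 that lasts longer, and Grade 4 that settles.

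**The concern.** Both sections tell a site when to stop and when it may restart, but they use different triggers and different approval steps. There is no cross-reference and no statement of precedence. Section 15.3 holds the grade-by-grade instructions, so an investigator with an abnormal laboratory result could follow it and never be pointed to 9.7.

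Two safeguards could be missed. A stage 2 subject who meets a liver stop criterion could stay on treatment because the event is low grade, awaiting a repeat test, or judged unrelated. Treatment could also be restarted after a liver-related hold without the sponsor agreement that 9.7 demands and, above 5x ULN, without the subject consent and IRB consultation that it calls for. The protocol itself treats one such patient as a major signal, so these rules should not be open to bypass through another section.

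**Working it through.** There is no sample size, power or error-rate figure to reproduce. The check sets the two sections side by side and counts.

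**Stopping, stage 2 subject meeting a 9.7 liver criterion**

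| Grade of the event | 9.7 | 15.3 |
|---|---|---|
| 1-2 | Stop | Continue; no liver exception |
| 3, repeat awaited | Stop | May continue at the investigator's judgment |
| 3, confirmed, related | Stop | Hold |
| 3, confirmed, probably not related | Stop | Case by case, at the investigator's discretion |
| 4, related | Stop | Withhold |
| 4, not related | Stop | No instruction |

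- 9.7 liver criteria with a causality condition: 0 of 4.
- 15.3 lines that first direct a hold (confirmed Grade 3; Grade 4) and depend on relatedness: 2 of 2.
- 9.7 liver criteria that start at 3x ULN: 2 of 4.

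The ALT/AST cut-offs for each grade do not appear in the document, so the grade of a given enzyme value has to be assumed. If a value just above 3x ULN is Grade 1-2, the instruction to continue contradicts 9.7 outright. If it is Grade 3 or 4, 15.3 leaves a not-related event to discretion or gives no instruction, where 9.7 says stop. Under either assumption, 15.3 offers a way to continue that 9.7 does not.

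**Restarting**

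| 15.3 restart line | Sponsor step in 15.3 | Required by 9.7 |
|---|---|---|
| Grade 3, settles to Grade 2 or less within 7 days | None | Agreement |
| Grade 3 lasting more than 7 days | Consultation; investigator decides | Agreement |
| Grade 4, settles to below Grade 2 within 7 days | Consultation; investigator decides | Agreement |

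- Lines requiring sponsor agreement: 0 of 3. Lines with consultation only: 2 of 3. Lines with no sponsor step: 1 of 3.
- Lines mentioning subject consent or the IRB: 0 of 3.
- 9.7 covers any interruption, so its agreement rule reaches 3 of 3.

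Section 15.3 does ask for notification: within 72 hours for a confirmed Grade 3 hold and within 24 hours for Grade 4. Notifying the team is not the same as obtaining agreement.

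**Who is affected.** Stage 1 visits ended in April 2018, so only stage 2 (target 300) is exposed. Stage 2 enrolment began in January 2019 in Malaysia and August 2019 in Thailand, treatment lasts 12 or 24 weeks, and this version is dated 18 March 2020. Some stage 2 subjects had therefore probably finished treatment already, and 300 is an upper bound.

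**The case against.** The best defence is that the two sections can be followed together. Section 9.7 is the specific rule and 15.3 the general scheme. Permission, discretion and silence in 15.3 do not cancel a mandatory stop, and section 19.5.5 binds investigators to the whole protocol. On this view the stopping half is only a missing cross-reference, and its one direct contradiction, at Grade 1-2, depends on grade cut-offs that are not shown.

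On restart, two of the three lines already involve the sponsor, so the gap there is consultation against agreement. Even the Grade 3 line with no sponsor step could be read as saying when restart becomes possible, with 9.7 adding the approval. Section 9.7 words the consent and IRB steps as what should be done, not what must be. The DSMB meeting and the 24- and 72-hour notices also make it likely that the team would know of a hold before a restart.

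Much of this stands. A site that reads both sections can comply with both, the plainest restart conflict is a single line, and the safeguards limit the harm. It does not remove the problem. The reading that the specific rule prevails is reasonable, but the protocol never states it. Notice of a hold does not secure agreement to a restart. A subject kept on treatment under 15.3 generates no hold to notify.

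**Conclusion.** The concern holds. Two stated safety rules disagree, and nothing in the protocol says which one governs. The clearest conflict is the restart line for Grade 3 settling within 7 days, which has no sponsor step although 9.7 requires agreement after any interruption. The other two restart lines fall short by asking for consultation only. On stopping, 15.3 has no exception for the stage 2 liver criteria and makes its directed holds depend on relatedness, which 9.7 does not.

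The size is modest. The counts describe the text and do not measure patient impact. At most the 300 stage 2 subjects are exposed, the number of liver events is not given, and no effect on SVR12 or any other endpoint is claimed. Whether the Grade 1-2 instruction contradicts 9.7 directly depends on the unshown grade cut-offs; the absence of a precedence rule and the restart gap do not.

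**What to change.** Change section 15.3 only:

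1. Open the action rules with a sentence such as: *These rules are subject to section 9.7; in stage 2 the liver stop criteria and rechallenge limits in 9.7 apply whatever the grade or causality.*
2. Add to the Grade 1-2 line: *unless a liver stop criterion in 9.7 is met.*
3. In all three restart lines, make restart conditional on being *agreed with the sponsor (see 9.7)*.

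The first sentence settles precedence. The other two edits put the rule on the lines a site will actually read when it acts.

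The cost is this wording and a memo to sites. Section 9.7, data collection and analysis do not change. Restarts after short Grade 3 holds would be slightly slower.

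One related point is left untouched. Section 5.3 excludes only AST/ALT above 10x ULN, so a subject enrolled at above 8x and up to 10x ULN already meets the first 9.7 criterion. The fix neither creates nor cures that.

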 - Patient has to have been on the same protocol-approved ARV regimen for ≥ 8 weeks prior to screening and is expected to continue the current ARV regimen through the end of study.
 - HIV ARVs: agents allowed in this study should be administered per the prescribing information in the package insert
 - Screening HIV RNA < 50 copies/mLⁱⁱ
 - Screening CD4 cell count ≥ 100 cells/uL
 - O HIV/HCV co-infected patients not receiving cART: Screening CD4 cell count must be ≥ 500 cells/uL

ⁱ To avoid he possibility of Immune reconstitution inflammatory syndrome - IRIS

ⁱⁱ This would allow us to properly evaluate the risk of virological failure during therapy

Exclusion criteria

- Decompensated cirrhosis defined as:
- Evidence of advanced stage liver cirrhosis and Child-Turcotte-Pugh (CTP) Class B or C or CTP score >6) or current/past history of decompensation including ascites, variceal bleeding, spontaneous bacterial peritonitis, or hepatic encephalopathy.
- Hepatocellular carcinoma: for all patients with cirrhosis, hepatocellular carcinoma (HCC), should be excluded by liver imaging within 6 months prior to screening, and this must continue periodically as in routine HCC surveillance.
- Laboratory exclusion criteria:
 - cirrhotic subjects with albumin < 2.8 g/dL
 - direct bilirubin > 3xULN
 - AST, ALT > 10xULN
 - Low neutrophil count (≤599 cells/mm³), hemoglobin (<9.0 g/dL for male, <8.5 g/dL for female), platelets (<50000 cells/mm³) classified as ≥ Grade 3
 - Patients with serum creatinine > 1.5 ULN or end stage renal disease^[2]
- Hepatitis B co-infection (HBsAg positive)
- Pregnancy, as documented by positive pregnancy tests at screening or baseline
- Breastfeeding

•

- Subjects currently receiving (or unable to stop the use for at least 1 week prior to receiving the first dose of study drug) any medications or herbal supplements known to be potent inhibitors or moderate inducers of cytochrome P450 (CYP) 3A4 or potent inducers of Pglycoprotein. This includes subjects who are on amiodarone or other contraindicated/excluded drugs (see section 9.3).
- Participation in other clinical trials within 3 months

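### Stage 2 entry allows ALT/AST up to 10x ULN, but the >8x and >5x stop criteria ignore baseline, so an eligible subject can meet them with stable or falling values

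*Protocol*

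**What the plan says.** **Entry.** The synopsis and Section 5.3 both set the liver-enzyme exclusion at "AST, ALT > 10xULN". It carries no stage qualifier, although the drug-use exclusion in the same list is marked as Stage 2 only. Section 16.1.2 describes the Stage 2 design as unchanged. A Stage 2 subject at or below 10x ULN is therefore eligible on this criterion.

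**Stopping.** Section 9.7 lists stop criteria that "will apply for any patient from stage 2 study". The first is "ALT/AST > 8x ULN" and the second is "ALT/AST remains > 5x ULN over 2 wks". Two further criteria start at 3x ULN but also need raised bilirubin or INR, or symptoms or eosinophilia. None mentions baseline, nadir or a change on treatment.

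**Consequences.** A DSMB meeting is convened "in case one patient meets any of the above listed criteria, which is considered as a major safety signal". On resuming treatment, Section 9.7 says "Restart of treatment after any interruption must be discussed and agreed on a case by case basis with the investigator" and adds that the sponsor must agree. As a general rule, "rechallenge of subjects with significant ALT/AST elevations (>5xULN) should not be attempted". Exceptions are possible for important benefit without other options, or on reassuring accumulated data. The subject must then be told of the risk and "consent to the rechallenge, and the institutional review board consulted".

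**The concern.** A stop rule for liver injury is meant to detect harm from the drug. Here the first two limits lie inside the range that the entry criteria accept, so they can be met by the disease that brought the subject into the trial. Section 11 itself anticipates raised baselines, since it plans to assess ALT and AST normalization from values above ULN.

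Elsewhere the protocol looks for change or causality. Section 15.1.1 counts a laboratory abnormality as an adverse event only if it appears or worsens on treatment. Section 15.3 ties a Grade 3 laboratory hold to a confirmed repeat and at least possible relatedness. The Section 9.7 criteria ask for neither, so an unchanged value that is not an adverse event can still be a stop event.

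At stake are an interruption of curative treatment without any worsening on drug, and a DSMB signal that does not separate a stable high baseline from new injury.

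**Working it through.** No sample size, power or alpha is involved, and the plan states no figure to reproduce. The check sets the limits side by side.

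**Inputs.** Entry limit: at most 10x ULN (synopsis, Section 5.3). Stop limits: above 8x, and above 5x over 2 weeks (Section 9.7). Chemistry at screening, Day 1, Week 4 and Week 8, not at Week 1 (Sections 7.1 and 7.2). Window of 7 days either side at Weeks 4 and 8 (Section 13.4).

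**Step 1: overlap if values do not change.**

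| Entry value (x ULN) | Eligible | Meets >8x | Meets >5x if it persists 2 weeks |
|---|---|---|---|
| 4.9 | yes | no | no |
| 5.1 | yes | no | yes |
| 8.0 | yes | no | yes |
| 8.1 | yes | yes | yes |
| 10.0 | yes | yes | yes |
| 10.1 | no | – | – |

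The exposed entry ranges are above 8x up to 10x for the first criterion, and above 5x up to 10x for the second.

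**Step 2: fall needed to avoid each criterion** = 1 − limit/entry.

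- Limit 8x: from 8.5x, 1 − 8/8.5 = 5.9%; from 9x, 1 − 8/9 = 11.1%; from 10x, 1 − 8/10 = 20%.
- Limit 5x: from 6x, 1 − 5/6 = 16.7%; from 8x, 1 − 5/8 = 37.5%; from 10x, 1 − 5/10 = 50%.

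Smaller improvements still count as stop events. From 10x to 8.5x is a 15% fall and meets the first criterion. From 10x to 5.5x is a 45% fall and meets the second if it persists.

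**Step 3: timing.** After Day 1 the first scheduled chemistry is Week 4, day 28 ± 7, so days 21 to 35. At nominal Week 4, (12 − 4)/12 = 67% of a 12-week course or (24 − 4)/24 = 83% of a 24-week course remains. Without an unscheduled test, the second criterion needs Weeks 4 and 8 both above 5x. These are nominally 28 days apart, or 14 to 42 days with both windows. Day 1 and Week 4 would suffice if Day 1 counts, which the text does not say.

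**Step 4: scale, under assumption only.** Let p be the share of 300 Stage 2 subjects who enter above 8x ULN and stay there. The protocol does not give p. The chance of at least one DSMB trigger without any rise is 1 − (1 − p)^300.

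| Assumed p | Expected subjects | Chance of at least one trigger |
|---|---|---|
| 0.1% | 0.3 | 26% |
| 0.5% | 1.5 | 78% |
| 1% | 3 | 95% |
| 2% | 6 | 99.8% |

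The range shows only that one trigger needs few such subjects. It is not an estimate of frequency.

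**The case against.** The strongest defence is that a fixed, conservative liver limit is a legitimate choice. Up to half of the subjects may be cirrhotic (Section 16.1.3). Planning to assess ALT and AST normalization implies that values are expected to fall, so a value still above 8x at Week 4 may deserve review whatever the baseline. Review routes exist: restart is decided case by case, rechallenge is possible under conditions, and the DSMB could look at the baseline chemistry. The investigator may also decline unstable patients at screening.

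Much of this stands. The routes soften the consequence, and over-stopping is the cautious direction of error. They do not prevent the stop or the DSMB trigger, and general discretion at screening does not replace an explicit 10x limit. The protocol does not say how fast values fall, and the rule takes no account of a partial fall. The criteria cite an external reference that is not at hand, so whether it expects a baseline adjustment cannot be judged here.

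The defence also rightly limits the remedy. A requirement for a rise across all criteria, for anyone with a raised Day 1 value, would lose real signals. A subject steady at 4x ULN with new bilirubin or INR dysfunction would no longer be stopped. Nor would one rising from 6x to 8.9x (8.9/6 − 1 = 48%) if the required multiple were 1.5, because the trigger becomes 1.5 × 6 = 9x.

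A reader might infer that the overlap will lower SVR12, or that stops will be common or permanent. The documents support none of these. They give no entry distribution or rate of fall, they allow restart, and Section 9.7 keeps subjects who stop in follow-up, so SVR12 can still be observed.

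**Conclusion.** The point holds as a mismatch between entry and stop limits. The first stop criterion can be met by an eligible subject entering above 8x and up to 10x ULN. The second can be met by one entering above 5x and up to 10x whose values stay above 5x over 2 weeks. In both cases values may be stable or improving. If the rule is followed, each such case means at least a temporary stop and a DSMB meeting.

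Confidence is high for this textual overlap, which rests only on the stated limits and the lack of any baseline reference or exemption. The number of subjects affected cannot be derived from the protocol, and no effect on SVR12 is claimed. The two criteria starting at 3x ULN also lack a baseline reference, but they need a second abnormality and are not part of the fault. The point is a cheap improvement of minor to moderate severity.

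**What to change.** Amend the protocol in one or both of these ways.

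1. **Align entry, for subjects not yet enrolled.** Set the Stage 2 ALT/AST entry limit no higher than the stop limits. A limit of at most 5x ULN removes both overlaps; at most 8x removes the first only.
2. **Qualify the stop rule narrowly.** Apply this only to subjects whose Day 1 value already exceeds the limit concerned (above 8x for the first criterion, above 5x for the second). For them, require a confirmed rise over the lowest value from Day 1 onward. Add an absolute cap at the 10x ULN entry limit, above which treatment always stops. Keep the fixed 8x limit for everyone entering at or below 8x, so that a rise from 6x to 8.9x still stops treatment. The lowest value is a better reference than baseline. A subject going from 9x to 2x and back to 8.5x has clearly risen from 2x, yet is still below the 9x baseline. The size of the rise should be agreed with the DSMB.

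Leave both criteria that start at 3x ULN unchanged. Show screening and Day 1 multiples of ULN beside each stop event sent to the DSMB.

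The cost is one amendment, using chemistry already collected at screening and Day 1. The downside is a slightly more complex rule under the second option, or a few otherwise eligible subjects excluded under the first.
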